8.3 Masking/Blinding of Study

This is an open-label pilot investigation. Masking and blinding procedures are not applicable.

9 Study Procedures

9.1 Visit 1 (Screening and Enrollment up to the day of surgery)

- Review of medical record
- Informed Consent - Patients will be identified during their preoperative appointment and introduced to a study; they will be provided with a copy of the consent document and information about the study. The consenting will take place after additional discussion on the day of surgery.

9.2 Visit 2 (Randomization and Treatment – day of surgery)

- Elective surgical procedure as per standard of care
- Intraoperative neuromuscular blockade, management, and neuromuscular antagonism will be at the discretion of the attending anesthesiologist.
- Upon arrival to the PACU, consenting patients will be randomized to have the TetraGraph placed on either their dominant or non-dominant arm. TetraGraph uses proprietary, single-use surface electrodes (TetraSens™, Senzime AB, Uppsala, Sweden) with stimulating electrodes placed over the ulnar nerve, a reference electrode placed on the adductor pollicis (1st digit) ([Figure 16.1](#)). The skin will be prepped with careful abrasion and cleansing of the skin in the usual fashion prior to electrode placement.
- ToFscan will be placed on the patient's opposite arm. Stimulating electrodes (Red Dot ECG electrodes, 3M, St. Paul, MN) will be placed over the ulnar nerve with the negative electrode near the wrist crease and positive electrode placed 3-4 cm proximally. The skin will be prepped with careful abrasion and cleansing of the skin in the usual fashion prior to electrode placement. The ToFscan utilizes a thumb splint with the encased transducer secured to the hand ([Figure 16.2](#)).
- To obtain measurements with TetraGraph, TOF stimulation will be performed at 50mA and the measurement recorded. This measurement will be repeated twice, 20 seconds apart. If the two measurements differ by >10%, a third measurement will be recorded, with the closest two readings kept and the outlier discarded. If TetraGraph yields a train-of-four count but not a ratio with any measurement, this will be recorded.
- To obtain ToFscan measurements, TOF stimulation will be performed and the measurement recorded. According to the manufacturer, the ToFscan does not require calibration, and the default stimulating current is 50 mA. The TOF measurement will be repeated twice, 20 seconds apart. If the measurements differ by >10%, a third measurement will be repeated, with the closest two readings kept and the outlier discarded. If TetraGraph yields a train-of-four count but not a ratio with any measurement, this will be recorded.
- Each neurostimulation with the TetraGraph and ToFscan will be conducted simultaneously with two observers. Patients will be queried as to the level of discomfort associated with obtaining measurements ([Figure 16.3](#)). We have previously utilized this scoring system for a large, multi-center volunteer trial (manuscript submitted). If patients are unable to quantify their discomfort, this will be documented.
- The above described process will be repeated for both monitors upon arrival to PACU and after 5 minutes and 10 minutes into the PACU stay.

- ToFscan is an FDA approved monitor, while TetraGraph is CE marked, but not FDA approved yet. If TOF ratios below 0.9 are obtained with the ToFscan at any point during this study, the attending anesthesiologist will be notified, as per usual clinical routine. Possible actions include continued monitoring and supportive care, additional reversal agent administration, or, in extreme cases of weakness, ventilatory support with bilevel positive airway pressure (BiPAP) or tracheal re-intubation.
- Following measurements obtained with both devices at these specified time intervals and assuming TOF ratio is >0.9 , the devices will be removed and the patient will proceed along the standard recovery pathway.
- If at any point the patient describes the discomfort associated with neurostimulation as a verbal numeric score of 7 or higher, the patient will be given the option to discontinue the study.
- Prior to discharge from PACU, patients will be asked to recall if they had a neurostimulation. If they do recall it, we will again query the level of discomfort associated with obtaining measurements ([Figure 16.3](#)).

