Title	Comparison of the ToFscan and TetraGraph during Recovery of Neuromuscular Function in the Post Anesthesia Care Unit
Running Title	ToFscan vs TetraGraph
Phase	N/A
Methodology	Randomized, Open-Label
Overall Study Duration	6 months
Subject Participation Duration	Less than 1 hour
Single or Multi-Site	Multicenter International
Objectives	The primary aim of this study is to assess the agreement and repeatability between TOF values obtained from ToFscan and TetraGraph
Number of Subjects	120 (40 per site)
Diagnosis and Main Inclusion Criteria	Patients undergoing an elective surgery and requiring administration of NMBA intraoperatively
Study Device	TetraGraph
Duration of Administration	Single stimulation of ulnar nerve repeated at specific intervals as outlined in the Study Procedures (Section 6.2)
Reference therapy	ToFscan
Statistical Methodology	This pilot study is meant to be descriptive and it aims to collect basic data for future larger study

4 Introduction

This document is a protocol for a human research study. This study will be carried out in accordance with the applicable United States government regulations and Mayo Clinic research policies and procedures.

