4.3 Risks and Benefits

- The benefits of using neuromuscular blockade monitoring devices:
Early detection of residual neuromuscular blockade
- The risks of using neuromuscular blockade monitoring devices:
Slight discomfort when electrical stimulation is administered

5 Study Objectives

Primary Objective

To assess the agreement and repeatability between TOF values obtained from the ToFscan and TetraGraph during recovery from neuromuscular blockade as measured upon arrival to the PACU, and then 5 (+5 min) and 10 (+10 min) minutes later.

Secondary Objective

Determine the incidence of postoperative residual weakness in the PACU (defined as TOFR <0.90).

Assess patient discomfort associated with each neurostimulation utilizing a verbal numeric rating scale (VNRS) from 0-10.

6 Study Design

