6.4 Primary Study Endpoints

The primary endpoint of the study will be the repeatability of values obtained by ToFscan and TetraGraph monitors.

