10.2 Statistical Methods

Descriptive Statistics

Analysis of agreement between the devices will be assessed using the method described by Bland and Altman (Olofson et al. 2015). The bias is defined as the mean difference of repeated measurements from the ToFscan and the TetraGraph obtained at the same time intervals. The limits of agreement are defined as $\text{bias} \pm 2 \text{ SD}$, where SD denotes the standard deviations of the differences. Limits of agreement are interpreted as the reference range within which 95% of the differences will lie. The bias and the limits of agreements surrounding the bias ($\pm 2 \text{ SD}$) will be calculated with 95% confidence intervals. Repeatability between the two devices at the various time intervals will also be assessed with significance defined as a p-value <0.05 .

Handling of Missing Data

This is a prospective study and therefore we do not anticipate any missing data. In the event of any unexpected missing data, no attempt to impute this missing data will be made; missing data will simply be treated as missing in the statistical analysis.

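### The closest-two-of-three rule in Section 9.2 shrinks any within-device repeatability SD computed from the kept readings, most for the noisier device

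*Combined protocol and SAP*

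**What the plan says.** Section 6.4 states: "The primary endpoint of the study will be the repeatability of values obtained by ToFscan and TetraGraph monitors". It gives no estimator.

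Section 9.2 sets the measurement rule. Each device takes two TOF readings 20 seconds apart, on arrival in the PACU and at 5 and 10 minutes. For TetraGraph: "If the two measurements differ by >10%, a third measurement will be recorded, with the closest two readings kept and the outlier discarded". For ToFscan: "If the measurements differ by >10%, a third measurement will be repeated, with the closest two readings kept and the outlier discarded". Each device's own readings trigger its rule. Neither bullet says whether 10% is relative or in TOF-ratio units.

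Section 10.2 describes a Bland-Altman analysis: "The bias is defined as the mean difference of repeated measurements from the ToFscan and the TetraGraph obtained at the same time intervals". On repeatability it says only this, with a p-value threshold of 0.05: "Repeatability between the two devices at the various time intervals will also be assessed". It does not mention the third reading or the discard rule, and it defines no repeatability SD or coefficient.

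The synopsis ("The primary aim of this study is to assess the agreement and repeatability between TOF values obtained from ToFscan and TetraGraph") and the primary objective in Section 5 also word repeatability as a property between the devices. The PACU form in Section 18.3 has fields for readings #1, #2 and, if needed, #3, for each device and time point.

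**The concern.** The difference between two readings taken 20 seconds apart on one device is the raw material of within-device repeatability. Section 9.2 uses that same difference as a trigger. When it is large, it is replaced by the smallest of three pairwise differences. If the kept pair is the analysis dataset, as Section 9.2 read literally implies, the evidence of poor repeatability is removed before repeatability is estimated.

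Two things are at stake. First, the loss is greater for a less precise device, so a real difference between the devices is compressed. Section 4.1 expects accelerometry to be disturbed by movement in awake patients and EMG not to be, so the rule would hide part of the contrast that motivates the study. Second, the synopsis says the pilot is to supply basic data for a larger study. An SD carried forward would be too small unless that study used the same closest-two rule.

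**Working it through.** **The plan's own figures.** The plan gives no repeatability SD or coefficient to reproduce. Its only SD is the 0.07 in Section 10.1, from volunteers with another AMG device and not identified as within-device. It serves below only as a bound.

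**Direction.** Let d₁₂ = |x₁ − x₂|. If d₁₂ is within 10%, it is kept. Otherwise the kept difference is min(d₁₂, d₁₃, d₂₃), which cannot exceed d₁₂. With SD = √(mean d² / 2), the kept-pair SD therefore cannot exceed the SD from readings #1 and #2 as taken. This step needs no distributional assumption.

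**Size.** Monte Carlo, 2 to 4 million triplets per setting. Readings are independent N(0.90, s), with the true ratio constant over the replicates. The third reading is used if d₁₂ exceeds 10% of the pair mean (relative) or 0.10 (absolute).

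| True SD s | Kept / true, relative | Kept / true, absolute |
|---|---|---|
| 0.02 | 0.992 | 0.998 |
| 0.025 | 0.959 | 0.979 |
| 0.03 | 0.899 | 0.937 |
| 0.035 | 0.828 | 0.878 |
| 0.04 | 0.759 | 0.815 |
| 0.05 | 0.644 | 0.696 |
| 0.07 | 0.515 | 0.547 |

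Readings #1 and #2 as taken return the true SD in every row. The share of pairs needing a third reading is 3.4% / 1.8% at 0.03, 11% / 8% at 0.04 and 20% / 16% at 0.05.

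As a repeatability coefficient (1.96 × √2 × SD = 2.77 × SD), at s = 0.05: 2.77 × 0.05 = 0.14 becomes 0.14 × 0.644 = 0.09 (relative) or 0.14 × 0.696 = 0.10 (absolute).

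**What 0.07 would allow.** If it is the SD of single-reading differences between equally noisy devices, each within-device SD is at most 0.07 / √2 = 0.049 (kept / true 0.654 / 0.707). With an assumed between-arm SD of 0.05, the bound is √((0.07² − 0.05²) / 2) = 0.035 (0.828 / 0.878). If it is the SD of differences of pair means, the bound is 0.07. PACU patients may differ from volunteers.

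**Device comparison.** Take true SDs of 0.04 and 0.02, a ratio of 2.0. Relative rule: (0.04 × 0.759) / (0.02 × 0.992) = 1.5. Absolute rule: (0.04 × 0.815) / (0.02 × 0.998) = 1.6.

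**Against sampling error.** 120 patients × 3 time points give 360 differences per device, so the 95% half-width for an SD is about 1.96 / √(2 × 360) = 7.3%. Over 3,000 simulated trials per setting, with patient-clustered standard errors, the interval from readings #1 and #2 covers the true SD in 94–95% of trials. The kept-pair interval covers it in 94–95% at 0.02, 75% / 91% at 0.025, 6% / 49% at 0.03 and 0% at 0.04 and above.

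**Meaning of 10%.** At a TOF ratio of 0.70 and s = 0.03, kept / true is 0.778 (relative) but 0.937 (absolute): a shrinkage of 22% against 6%.

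**Movement artefacts (assumed).** Core SD 0.03, with 5% or 10% of readings at SD 0.20. The SD of all readings is √(0.95 × 0.03² + 0.05 × 0.20²) = 0.053, or √(0.90 × 0.03² + 0.10 × 0.20²) = 0.069. Kept / true is 0.525 / 0.547 at 5% and 0.434 / 0.449 at 10%, so the kept-pair SD is 0.028 to 0.031.

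**The case against.** The strongest reply is that the biased statistic is not in the plan. No section specifies a within-device SD, and the synopsis, Section 5 and Section 10.2 all speak of repeatability between devices. That is correct and limits the point to within-device repeatability of replicate readings. But Section 6.4 names repeatability of the monitors' values as the primary endpoint, paired replicates are the data collected, and nothing in Section 10.2 prevents the kept pair from being used.

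Second, the rule may be meant to remove movement artefact. In the artefact scenario the kept-pair SD of 0.028 to 0.031 comes close to the assumed artefact-free 0.03. So the shrinkage there is an error only if repeatability is to describe readings as obtained in the PACU. That is a choice of estimand, and the plan does not make it. With plain normal noise and no artefact, the shrinkage remains.

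Third, the size is assumed. This stands: at 0.02 the effect is negligible, and at 0.03 under the absolute rule the 6% shrinkage is slightly below the 7.3% half-width. If variances differ between patients (assumed coefficient of variation 1), the half-width widens to about 13%. However, kept-pair coverage at 0.03 is then 0.00 / 0.02, so the problem does not go away.

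Fourth, pooling all recorded readings by degrees of freedom is also unbiased. That holds for normal errors, but under the 5% artefact scenario it gives 0.058 against a true 0.053. Readings #1 and #2 as taken remain unbiased in both.

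Last, no data are lost, because the form holds all three readings. This makes the fix cheap but does not make it unnecessary: Section 9.2 calls for discarding the reading, and Section 10.2 does not restore it.

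**Conclusion.** The point holds and should be fixed before analysis. Its direction is certain for any within-device SD or coefficient computed from the kept pair. Its size depends on a within-device SD that the documents do not give. It is negligible at about 0.02, comparable with sampling error at about 0.03, and dominant from 0.04 upward (24% / 18% shrinkage at 0.04). These figures assume a TOF ratio of 0.90 and independent normal errors. At equal TOF level the less precise device loses more, so the comparison between devices is compressed.

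The point does not extend to the mean bias between devices, which the rule leaves essentially unchanged. Nor does it claim a fixed direction for the limits of agreement.

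**What to change.** In Section 10.2:

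- Define primary within-device repeatability from readings #1 and #2 as taken, per device and time point, whether or not a third was triggered: SD = √(sum of squared differences / 2n), coefficient = 2.77 × SD. Use confidence intervals that allow for repeated time points within a patient, for example a bootstrap resampling patients.
- Give closest-two repeatability only as a labelled sensitivity analysis.
- Report, by device, the share of pairs needing a third reading and the share with a count but no ratio, which cannot enter the SD.
- State what repeatability between the two devices means, if it is a separate quantity.
- State which readings enter the Bland-Altman analysis, with the other choice as a sensitivity analysis. The primary agreement analysis need not change.

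In Section 9.2:

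- Say that all three readings are retained, and whether 10% is relative or in absolute TOF-ratio units.
- The ToFscan bullet repeats "If TetraGraph yields a train-of-four count but not a ratio with any measurement, this will be recorded"; state that this also covers ToFscan.

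The cost is wording only, with no new measurement and no new form field. The downside is that reported repeatability may look less favourable, and readings with movement artefact stay in the primary estimate.

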9.3 Schedule of Events

Schedule of Events		
Study Activity	Visit 1	Visit 2
ToFscan and Tetraphraph		X
Informed consent	X	
Review of Medical Record	X	
Adverse event evaluation		X

10 Statistical Plan

10.1 Sample Size Determination

Based on paired t-test, 23 enrolled patients will give 90% power to detect a difference in TOF ratios with a significance level of 0.05 (JMP Pro Software version 13.0.0 [August 23, 2018]; SAS Institute Inc., Cary, NC). We utilized a standard deviation of 0.07 that was determined during our multi-center volunteer study comparing another AMG device and TetraGraph. However, we will enroll 40 patients at 3 sites for a total of 120 patients to account for dropout during the study and to provide further insight into the incidence of postoperative residual weakness and three large centers. The other centers that might be submitting similar studies and

sharing de-identified data for the purposes of data analysis and publication are as follows:

NorthShore University HealthSystem, Evanston, IL, USA [REDACTED]

[REDACTED] and University of Debrecen, Debrecen,

Hungary [REDACTED]. Each

site will complete separate applications for their IRB or Ethics committee approval; Mayo Clinic in Florida will serve as the lead site and will provide oversight to ensure compliance with the protocol at each site. .

10.2 Statistical Methods

Descriptive Statistics

Analysis of agreement between the devices will be assessed using the method described by Bland and Altman (Olofson et al. 2015). The bias is defined as the mean difference of repeated measurements from the ToFscan and the TetraGraph obtained at the same time intervals. The limits of agreement are defined as $\text{bias} \pm 2 \text{ SD}$, where SD denotes the standard deviations of the differences. Limits of agreement are interpreted as the reference range within which 95% of the differences will lie. The bias and the limits of agreements surrounding the bias ($\pm 2 \text{ SD}$) will be calculated with 95% confidence intervals. Repeatability between the two devices at the various time intervals will also be assessed with significance defined as a p-value <0.05 .

Handling of Missing Data

This is a prospective study and therefore we do not anticipate any missing data. In the event of any unexpected missing data, no attempt to impute this missing data will be made; missing data will simply be treated as missing in the statistical analysis.

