4.1 Abstract

Residual neuromuscular blockade is a common occurrence in the post-anesthesia care unit (PACU) when neuromuscular blocking agents (NMBAs) have been used in the operating room. The only method of reliably detecting residual neuromuscular blockade is through the use of quantitative neuromuscular monitors. Unfortunately, several barriers exist that have prevented the widespread application of these devices. For instance, there is a paucity of quantitative neuromuscular monitors commercially available. Also, two modalities of quantitative monitoring, kinemyography and acceleromyography, rely on movement of the muscles of interest, a characteristic frequently compromised during patient positioning for surgical procedures or in uncooperative awake patients in the PACU. Additionally, many clinicians are unfamiliar with these quantitative monitors, and incorporating them into their practice can represent an undesirable educational burden. The aim of this investigation is to compare the performance of two quantitative monitors utilized on post-anesthesia recovering patients. The ToFscan (Draeger Medical Inc., Telford, PA) represents one of the few standalone acceleromyography (AMG)-based quantitative monitors available for routine clinical use in the United States. The TetraGraph (Senzime AB, Uppsala, Sweden) is a standalone electromyography (EMG)-based quantitative monitor that recently received Conformité Européene (CE) approval. While both of these quantitative monitors can be utilized to guide intraoperative NMBA re-dosing and confirm recovery, they provide their objective data via drastically different techniques. AMG, based on Newton's Second law which describes force being proportional to acceleration, measures acceleration of the thumb and requires its unobstructed movement. As such, performing AMG in awake, uncooperative patients can yield inaccurate results because of unwanted patient movement. Alternatively, EMG measures electrical activity within the muscle following peripheral nerve stimulation, and is unaffected by involuntary patient motion. We plan to compare measurements with these two devices throughout various stages of neuromuscular recovery in the PACU and compare the usefulness of these devices in this vulnerable patient population.

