Utilizing recommendations from the Good Clinical Practice (GCP) Guidelines for monitoring of neuromuscular function (Fuchs-Buder et al. 2007), we will investigate the performance of the TetraGraph in patients recovering from anesthesia in the PACU. The postoperative setting is particularly important, as several previous studies performed in awakening patients have reported discordant TOF ratios: accelerographic TOF ratios were not an accurate representation of the neuromuscular status (recovery) of the patients (Baillard et al. 2004). We plan to compare two portable quantitative monitors, the EMG-based TetraGraph and the AMG-based ToFscan. ToFscan has recently been described as an acceptable surrogate for research purposes to the frequently used TOF-Watch (Murphy et al. 2018). The TOF-Watch monitor, however, is no longer manufactured, while the ToFscan is commercially available and approved by the United States Food and Drug Administration (FDA). While the ToFscan has a three-dimensional sensor that can measure acceleration in multiple planes, it still has the same limitations associated with muscle movement inherent to AMG-based quantitative monitors. This is of particular importance in the recovery room when patients may not be fully cooperative when quantitative monitoring is warranted to exclude postoperative residual weakness as a cause of patient distress.

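### Section 10.2 plans constant-width limits of agreement with no check that bias and spread are constant across TOF ratio, so coverage within a recovery range could be off in either direction

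*Combined protocol and SAP*

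**What the plan says.** Section 10.2 (Statistical Methods) assesses agreement by the Bland-Altman method. On the bias it says: "The bias is defined as the mean difference of repeated measurements from the ToFscan and the TetraGraph obtained at the same time intervals". The limits are the bias plus and minus 2 SD, "where SD denotes the standard deviations of the differences". Their meaning is then stated: "Limits of agreement are interpreted as the reference range within which 95% of the differences will lie". Bias and limits are to carry 95% confidence intervals.

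The section does not say whether one set of limits pools all time points or each time point (arrival, 5 minutes, 10 minutes) has its own. Under either reading the band has the same centre and width at every TOF ratio. No plot or test of dependence on level is planned, and there is no transformation, no regression-based limits and no limits by TOF band. The section cites a paper on advanced Bland-Altman methods, but the formula written down is the simple one.

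Agreement is part of the primary objective (section 5). The abstract (section 4.1) says: "We plan to compare measurements with these two devices throughout various stages of neuromuscular recovery in the PACU". A ratio below 0.90 defines residual weakness in section 5, and in section 9.2 a ToFscan ratio below 0.9 leads to notification of the attending anesthesiologist.

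**The concern.** A constant band describes agreement at a given TOF ratio only if the mean and spread of the differences do not change with that ratio. The two devices measure different things, thumb acceleration and muscle electrical activity, so constancy cannot be taken for granted. The study also plans to sample more than one stage of recovery.

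Readers will apply the published limits near 0.90, because that is where the protocol draws its line. If spread or bias changes with level, the band will be too narrow in one part of the range and too wide in another. The pooled summary would not show this, because overall coverage can stay near 95% throughout. The limits are also the main descriptive output of a pilot meant to inform a larger study, so an unnoticed dependence on level would carry forward.

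**Working it through.** **Inputs.** From the documents: limits at bias ± 2 SD, read as a 95% range (section 10.2); the cut-off of 0.90 (section 5); and one SD, 0.07, in section 10.1: "We utilized a standard deviation of 0.07 that was determined during our multi-center volunteer study comparing another AMG device and TetraGraph". It is a single value, from a different acceleromyography device and from volunteers, and is not broken down by recovery level. Assumed, because the documents give nothing: the share p of readings below 0.90, the SD below (s_L) and above (s_H), and any shift in bias d between the two groups.

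**1. The plan's own figure.** For normal differences with constant bias and SD, coverage of ± 2 SD is 2Φ(2) − 1 = 95.45%. The plan's 95% is right on those terms. At SD 0.07 the half-width is 2 × 0.07 = 0.14.

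**2. Two groups, equal bias, different SD.** Pooled SD S = √(p·s_L² + (1 − p)·s_H²). Coverage in a group with SD s is 2Φ(2S/s) − 1. Take p = 0.30.

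- Larger spread below, 0.12 / 0.05: S = √(0.3 × 0.0144 + 0.7 × 0.0025) = √0.00607 = 0.0779, limits ± 0.156. Below: 2Φ(0.156/0.12) − 1 = 80.6%. Above: 2Φ(0.156/0.05) − 1 = 99.8%. Overall: 0.3 × 0.806 + 0.7 × 0.998 = 94.0%.
- Smaller spread below, 0.035 / 0.07: S = √(0.3 × 0.001225 + 0.7 × 0.0049) = √0.0037975 = 0.0616, limits ± 0.123. Below: 2Φ(0.123/0.035) − 1 = about 100%. Above: 2Φ(0.123/0.07) − 1 = about 92%. Overall: 0.3 × 0.9996 + 0.7 × 0.922 = 94.5%.
- Mild difference, 0.09 / 0.07: S = √(0.3 × 0.0081 + 0.7 × 0.0049) = √0.00586 = 0.0766, limits ± 0.153. Coverage is 91% below, 97% above and 95.3% overall.

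| SD below / above 0.90 (assumed) | Limits | Below | Above | Overall |
|---|---|---|---|---|
| 0.12 / 0.05 | ± 0.156 | 80.6% | 99.8% | 94.0% |
| 0.09 / 0.07 | ± 0.153 | 91% | 97% | 95.3% |
| 0.035 / 0.07 | ± 0.123 | about 100% | 92% | 94.5% |

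**3. Equal SD, shifted bias.** With SD 0.07 in both groups, p = 0.20 and d = 0.10, the pooled bias is 0.02 and S = √(0.0049 + 0.2 × 0.8 × 0.01) = √0.0065 = 0.0806, so the half-width is 0.161. Coverage in the low group is Φ((0.02 + 0.161 − 0.10)/0.07) − Φ((0.02 − 0.161 − 0.10)/0.07) = 87.7%. It is 97.3% in the high group and 95.4% overall.

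**4. Range.** Keep s_H = 0.07 and let p run from 10% to 40%. With s_L 1.5 to 3 times as large and d from 0 to 0.10, low-ratio coverage runs from 61% to 90% while overall coverage stays between 93% and 96%. With s_L half as large and d = 0, low-ratio coverage is about 100% and high-ratio coverage runs from 91% to 95%.

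**The case against.** The strongest reply is that section 10.2 speaks of 95% of the differences, which is a statement about all of them together. A reader might infer from the missing check that this statement is false. The documents do not support that, and nor does the arithmetic: overall coverage stays at about 94% to 95% in every scenario worked through above and at 93% to 96% over the wider range. This part of the objection stands. What is open to doubt is coverage within a TOF range.

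A reader might also infer that the limits will fail specifically in weak patients. No passage gives bias or spread by recovery level. The background (section 4.2) reports of awakening patients that "accelerographic TOF ratios were not an accurate representation of the neuromuscular status (recovery) of the patients", but it ties this to movement and cooperation and does not link it to the level of the TOF ratio. Nor does the rule in section 9.2 for a third reading when two differ by more than 10% help. If the 10% is relative, it suits error that grows with the ratio, and so smaller spread at low ratios. The text does not say whether it is relative or in percentage points. The direction is therefore unknown.

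Finally, the synopsis calls this a descriptive pilot, no pass/fail decision rests on the limits, and dependence on level could be examined later from the same data. That keeps the point from being serious, but does not dispose of it. The limits are the main descriptive result, and a method fixed beforehand is stronger than one chosen after seeing the plot.

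**Conclusion.** The concern holds as a conditional one. Section 10.2 writes down limits that are constant over TOF ratio, whether pooled or per time point, and plans nothing that would show whether constancy is reasonable. If it is not, the overall 95% figure remains about right while coverage within a TOF range can be too low or too high on either side of 0.90. The illustrations (81% / 99.8% one way, about 100% / 92% the other) rest on assumed SDs, an assumed 30% of readings below 0.90, and normal differences. They show what could happen and do not predict what this trial will find. If spread and bias prove constant, the planned limits are adequate as they stand. This is a cheap and worthwhile improvement, not a flaw that invalidates the analysis.

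**What to change.** Add to section 10.2:

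- State whether limits are pooled or per time point.
- Plot the difference against the mean of the two devices.
- Regress the difference on the mean, and the absolute residual on the mean. Use a mixed model or patient-clustered standard errors, because each patient gives up to three time points with two kept readings per device (sections 9.2 and 18.3). Intervals that ignore this could signal a trend wrongly.
- If either slope's 95% confidence interval excludes zero, report regression-based limits, read off at a TOF ratio of 0.90, alongside the constant limits.
- In all cases report bias and limits descriptively for mean TOF ratio below 0.90 and at or above 0.90, with 95% confidence intervals.
- Describe the overall 95% range as an average over the recovery levels actually sampled.

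No extra patients, readings or procedures are needed. The cost is a little more analysis and imprecise limits in a small stratum. As a guide, with one difference per patient and SD 0.07, the 95% interval around a limit is about ± 1.96 × 0.07 × √(1/n + 4/(2(n − 1))). That is ± 0.022 for n = 120, ± 0.038 for n = 40 and ± 0.050 for n = 23. The number of readings below 0.90 is not known in advance, so the stratum results should be labelled descriptive.
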